Target hospitals	1) Primary care hospital for stroke management 2) Secondary care hospital for stroke management 3) Tertiary care hospital for stroke management
Objectives and research questions	
Objective 1: Describe performance of care and services based on measurement of clinical and organizational quality indicators of acute stroke care in differently designated Quebec hospitals (primary, secondary and tertiary).
 
Research question 1: What is performance of care and services based on measurement of clinical and organizational quality indicators of acute stroke care in differently designated Quebec hospitals (primary, secondary and tertiary)?
 
Objective 2: Identify the sociodemographic and clinical characteristics of patients that may influence results regarding measurement of clinical and organizational quality indicators of acute stroke care.
 
Research question 2: What are the sociodemographic and clinical characteristics of patients that may influence results regarding measurement of clinical and organizational quality indicators of acute stroke care?

Target population	
Adults with ischemic stroke
 
All persons hospitalized for ischemic stroke within the 6 months preceding approval of the Research Ethics Board (REB). The study will be conducted based on their health records.

Inclusion criteria	Adults 18 years old or over with ischemic stroke requiring hospitalization in an acute care unit or special stroke unit
Exclusion criteria	Adults with hemorrhagic stroke
Type of study	Retrospective descriptive-correlational study
Period covered by study	6-month period preceding approval of the REB
Sample size	
Given that about 660 patients are hospitalized for ischemic stroke each year in the three hospitals under study and the data will be collected over a period of 6 months, sample size is estimated to be about 130 health records.
 
Because the minimal effect size is not known, an effect size of 50 % is used. A power calculation in G*Power on analyses of group averages indicates

	
this sample size is largely sufficient to have a power of 95 %, an alpha set at 0.05 and a minimal effect size of 0.5. The number of patient records retained will provide a sample representative of the hospitalized population in the three hospitals.
 
Finally, a records evaluation test (n=6) will be performed in advance to estimate the time needed to examine each record and allow needed adjustments to be made to conduct research within the context of a doctoral study.

Data collection	
Results measurement:
 
 • Retrospective data collection performed on patients' health records included in the study (patients' sociodemographic and clinical data, results of evaluation of clinical and organizational quality indicators) • Description of hospitals through data collected on their characteristics based on an analysis of the environment and context of the different centers. This data collection will be performed using a structured interview guide (targeted questions) to identify hospitals' characteristics according to the clinical documentation and consultations with various clinicians, managers and doctors available in the centers under study.
Data analysis	
Statistical analyses will be conducted using SPSS software to meet the study's objectives.
 
Objective 1: Retrospective descriptive analysis based on patients' health records
 
Objective 2: Univariate and multivariate analyses; type of analysis based on type of variable (linear and logistical) and according to distribution (parametric and nonparametric tests)

Anticipated impacts	
 • Broaden the state of knowledge regarding acute ischemic stroke by drawing a picture of stroke patient management in three differently designated Quebec hospitals; • Identify the sociodemographic and clinical determinants that may influence the results of certain indicators; • In the long term, this project may contribute to reduce the gap between current practices and guidelines regarding post-acute stroke management; • Optimize acute stroke care and services across Quebec through improved understanding of different hospital contexts.

1. Introduction

In Canada, ischemic stroke is the fourth leading cause of death (Statistics Canada, 2020) and one of the main causes of severe disability in adults (Krueger et al., 2015). The literature clearly shows that rapid management, access to revascularization treatments and an offer of structured, well-coordinated care are necessary, even essential, for the physical, cognitive and psychological recovery of persons experiencing a stroke (Boulanger et al., 2018). In Quebec, ischemic stroke is the most common cause of hospitalization (Institut national de santé publique du Québec [INSPQ], 2018). An increase of about 17,000 hospitalized patients was identified, notably, in the decade between 2003-2004 and 2013-2014, representing an increase of about 46 % accompanied by a parallel rise in the needs for care and services for these patients (INSPQ, 2018).

To ensure equity and quality of care and services at the national level, Canadian and international guidelines are regularly published, disseminated and updated consistent with evolution of the state of knowledge regarding, notably, ischemic stroke. These guidelines are deployed on a continuum of stroke-related care and services involving six phases: 1) public awareness raising, 2) primary prevention, 3) hyperacute management, 4) acute management, 5) rehabilitation, and 6) return and maintenance in the community. This continuum guides the offer of care and services and contributes to optimal follow-up in persons with stroke or at risk of stroke and their caregivers concerning immediate recognition of signs of stroke, rapid restoration of blood flow to the brain with hyperacute revascularization treatments, and organization of care and services based on predefined care trajectories (Ministère de la Santé et des Services Sociaux [MSSS], 2017a). In ischemic stroke, the first aim of treatment is to restore blood flow to the brain as rapidly as possible in order to limit deficits and thus facilitate early rehabilitation supported by caregivers. For a number of years now, the administration of intravenous thrombolysis (IVT) to dissolve blood clots obstructing blood vessels has been the first treatment of choice for persons with ischemic stroke who meet eligibility criteria (Adams et al., 2007; Boulanger et al., 2018; Lindsay et al., 2005). In addition to type of stroke, the main eligibility criterion involves access to the treatment within 4.5 hours from onset of symptoms, which unfortunately restricts its administration (Boulanger et al., 2018; Wardlaw et al., 2014). Studies conducted in Canada report certain issues regarding IVT. Notably, in Québec, in 2016, the Institut national d'excellence en santé et services sociaux (INESSS) revealed that 23 % of all candidates in the province considered eligible for thrombolysis IV had received the treatment (INESSS, 2016). With the advance in treatments since 2015, thrombectomy, which involves removing clots blocking an artery with specialized devices, has become an additional recognized, privileged practice for treating ischemic stroke caused by obstruction of the large vessels (Goyal et al., 2016; Menon et al., 2016; Vidale et Agostoni, 2017). In Quebec, this type of treatment is available in tertiary hospital centers, i.e., specialized centers offering neurointervention. However, according to

the data collected by the INESSS in 2013-2014, of the 3,134 persons admitted for stroke in 70 hospitals in Quebec, only 14.2 % presented in a tertiary center for symptoms of stroke (INESSS, 2014). This indicates that the majority of those with ischemic stroke must be transferred to access this advanced treatment. In 2017-2018, in Quebec, the rate of thrombectomy was 4.5 %, while the anticipated rate of potentially eligible patients rose to about 10 % (INESSS, 2019). Accordingly, different care trajectories are envisaged to promote accessibility to optimal treatments based on geographic location, eligibility criteria and available resources.

To date, the international literature has highlighted hyperacute stroke management regarding accessibility of and equity of access to revascularization treatments, an issue even in Canada (Eswaradass et al., 2017). Although the hyperacute phase is important and therefore extensively documented, guidelines maintain that the acute phase including early rehabilitation is also paramount in the post-stroke care trajectory to foster the ongoing improvement of cognitive, language and functional capabilities (Boulanger et al., 2018; Teasell et al., 2019).

The acute phase involves hospitalization in an acute care unit of a patient with ischemic stroke whose revascularization treatment may have been administered based on their clinical condition. It generally occurs within the seven days following the stroke, and its duration may vary consistent with the patient's state of health and needs for care and services. Favorably involving admission to a special stroke unit depending on the designation of the patient's hospital and its available resources, this phase also includes early rehabilitation and the implementation of an interdisciplinary intervention plan carried out by a team composed of different clinicians in collaboration with the patient and caregivers. Finally, this phase also involves referral based on the patient's needs including inpatient or outpatient rehabilitation and secondary prevention to limit the risk of a recurrent attack (MSSS, 2017a). In Québec, in the last decade, only two studies of the acute phase evaluated patient management to discern if clinical practice regarding certain interventions complied with Canadian guidelines. In fact, a provincial field assessment conducted in 2013-2014 revealed that only 14 % of patients had been admitted to a stroke care unit and that screening for dysphagia using a standardized tool was registered in only 16 % of patient records (INESSS, 2016). Furthermore, in 2015-2016, a regional study conducted in a hospital in Centre-du-Québec revealed that screening for dysphagia using a standardized tool was performed in 65% of the cases analyzed and that screening for risk of falls was recorded for 29 % of these same cases (Bélanger and Cloutier, 2021). Moreover, in addition to the introduction of thrombectomy in 2015 in Quebec, which called for the reorganization of certain care and services, modifications surrounding the governance of the health system subsequent to Bill 90 (which modified existing organizational structures for patient care) produced substantial changes in terms of accessibility and offer of care and services (MSSS, 2014). Since then, no study has evaluated acute stroke clinical practice in the province. Furthermore, reports describe the clinical and organizational effects

of the Covid-19 pandemic since 2020, which potentially influence the decisions of managers, role of the clinical staff and involvement of families and caregivers during a stroke (Montaner et al., 2020; Rudilosso et al., 2020; Smith et al., 2020).

To optimize practice and support managers and clinicians in hospitals, experts have formulated recommendations aimed at enhancing the offer of care and services. These recommendations are regularly updated as the science evolves and enable a personalized action plan to implement within each organization depending on its mission. In terms of acute stroke, they stress the development of interdisciplinary approaches to improve management of stroke patients by outlining individualized interventions and including caregivers in care and decision-making. These interventions involve the evaluation of physical, mental and cognitive state of health, patient management, support for caregivers, and follow-up on the improvement or deterioration of cognitive, language and motor functioning in order to promote recovery, prevent the potential complications of a recurrent attack or offer palliative care if necessary (Boulanger et al., 2018; MSSS, 2017b; Powers et al., 2018; Teasell et al., 2019). To this effect, the authors of guidelines, scientific studies and the gray literature also propose numerous quality indicators to measure the results of an action plan and make needed adjustments at the clinical and organizational levels (Boulanger et al., 2018; MSSS, 2017b; Powers et al., 2018; Teasell et al., 2019). A quality indicator is defined as a reliable and valid measurement of a state of health, a practice or an organization of care (MSSS, 2012). Moreover, the current state of knowledge highlights certain discrepancies between the guidelines for achieving quality indicator targets associated with the time dependency of certain clinical medical interventions and practices related to the hyperacute management of patients with ischemic stroke in Quebec (INSPQ, 2019). Some such discrepancies are explained by, among other things, geographic and contextual issues based on types of patient management centers.

In Quebec, temporary designations have been issued for primary, secondary and tertiary care hospitals meeting the criteria established by the MSSS (MSSS, 2013). A primary care hospital can diagnose a stroke and offer revascularization treatments such as thrombolysis IV or telethrombolysis IV. A secondary care hospital can offer thrombolysis IV at any time and houses a stroke care unit with a rehabilitation team composed of different clinicians. In keeping with the criteria established by the ministry, these types of center should also provide follow-up with a secondary prevention clinic. Finally, a tertiary care hospital offers specialized neurovascular treatments including thrombectomy or neurosurgery (INESSS, 2016, 2019).

Researches, however, have highlighted disparities regarding types of hospitals managing stroke patients. One study in particular revealed that hospitals' profiles had a significant impact on patients' clinical results, mainly

because the availability of stroke units and number of patients admitted increased the exposure of clinicians and the medical team to stroke cases (Park et al., 2019). It also showed that hospitals with a higher level of care processes demonstrated improved performance of stroke healthcare based on measurement of quality indicators and therefore generated more favorable clinical results in patients, for example, a lower mortality rate (Yu-Chi et al., 2016). Moreover, a 10-year longitudinal study in the United States pointed to a persistent significant difference between rural and urban environments, the reason being rural patients' less privileged access to hyperacute revascularization treatments and a higher 90-day mortality rate (Wilcock et al., 2020). This difference was also observed in Canada through a higher 30-day post-stroke mortality rate in hospitals in rural areas compared with those in urban centers. However, the province of Quebec was not included in this study in which 89 % of the hospitals lacked tomography services and 79 % had no intensive care unit (Fleet et al., 2018). In Quebec, super-specialized (tertiary care) hospital centers are located in large cities, and hospitals in remote areas are less likely to have a stroke unit (INESSS, 2019). However the current state of knowledge does not allow for an overall picture of the issues surrounding acute stroke care in Quebec.

Other studies have focused on the clinical profiles of stroke patients as possible factors contributing to differences in measurement of quality indicators irrespective of the center where these patients are hospitalized. Notably, the severity of the stroke evaluated by the National Institute Health Stroke Scale (NIHSS), the state of consciousness, aphasia at admission and duration and type of symptoms at admission were associated with different time intervals for getting a CT scan or receiving hyperacute thrombolysis (Ungerer et al., 2020). However the current literature does not associate patients' clinical profile with the achievement of targets of certain acute stroke quality indicators. What's more, it points to sociodemographic characteristics such as age, sex and ethnicity as possible influences on the achievement of quality indicator targets and optimal patient management. Moreover, it appears that women receive fewer hyperacute revascularization treatments than men (Colello et al., 2018; Falsetti et al., 2017; Mainz et al., 2020; Strong et al., 2020) and that they generally take longer to present at the stroke unit compared with men, mainly because they wait longer to consult (Falsetti et al., 2017; Mainz et al., 2020). Reasons appear to be more advanced age and the higher proportion of women living alone when the stroke occurs (Mainz et al., 2020). Regarding the hyperacute phase, several other studies discuss the impact of age during revascularization treatments including the decisional process involved in administering a thrombectomy to patients above 80 years old and the post-treatment clinical results of these patients (Al-Mufti et al., 2021). Now, to our knowledge, no study has evaluated the impact of age on the achievement of targets regarding acute stroke quality indicators in Quebec. The national data of the Institut national de santé publique (INSPQ) show that the prevalence of ischemic stroke increases sharply with age in groups 50 years old and over (INSPQ, 2018). In addition

to sex and age, cultural differences are seen to influence the achievement of certain targets during measurement of quality indicators for stroke including mortality within a year and the administration of antithrombotics and statins for secondary prevention at discharge (Gardener et al., 2021).

These observations enable an understanding of the importance of evaluating practices using quality indicators to reduce the gap between acute stroke guidelines and practice. Prior to the present study, we conducted a scoping review of the Arskey and O'Malley methodological framework (2005) to identify the clinical and organizational indicators attributable to the acute phase. A total of 26 articles were included in the review and over 300 indicators were identified based on the grey literature, guidelines and scientific studies. A summary of these indicators followed. A stroke care advisory committee including a patient partner validated the indicators identified in the literature. This approach allowed us to identify 29 priority indicators to measure in clinical practice during the acute phase of the stroke continuum in terms of relevance, validity and feasibility. These clinical (n=19) and organizational (n=10) quality indicators were classified based on dimensions of care performance, namely, accessibility of services (accessibility and equity of access), optimization of resources (efficiency and viability) and quality of care (safety, effectiveness, continuity and reactivity) (Bélanger et al., 2024). Nevertheless, despite this broad inventory of acute stroke indicators, the way they have been validated, tested and integrated at the organizational level and in clinical practice remains unclear (Jolley et al., 2017).

Prior knowledge indicates that quality indicators have been generally measured using patients' health records to obtain a picture of the state of practices. Retrospective data collection is a method frequently employed in research and epidemiology to describe the achievement of quality indicator targets to evaluate the management of a large number of patients with a shared pathology or clinical condition (Simpson et al., 2017). When guidelines are issued in line with a particular care trajectory such as the stroke continuum of care, it's important for health records to show that all patients receive care and services in compliance with guidelines irrespective of their sociodemographic data, clinical profile or geographic location. Now, in Quebec, no study on the measurement of clinical and organizational indicators takes into account the context of the different patient care centers. Nor does the state of knowledge identify the sociodemographic and clinical determinants of patients that may influence the results of measurement of acute stroke quality indicators.

The aim of the present study is to get to discover the current state of acute stroke practice by evaluating the performance of stroke care and services based on measurement of clinical and organizational quality indicators. The achievement of these indicators during hospitalization for acute stroke in differently designated Quebec hospitals will be evaluated using patients' health records. This research project is consistent with the guidelines

of the Ministère de la Santé et des Services Sociaux (MSSS), which aims to improve the performance of the health system in terms of accessibility of services, quality of care and optimization of resources (MSSS, 2017b).

2. Objectives, questions and research hypotheses

The aim of this research project is to describe performance of care and services of acute stroke care in differently designated Quebec hospitals

1. Identify the sociodemographic and clinical characteristics of patients that may influence the results regarding measurement of clinical and organizational quality indicators of acute stroke care.

More specifically, this research project aims to answer the following questions:

1. What is performance of care and services based on measurement of clinical and organizational quality indicators of acute stroke care in differently designated Quebec hospitals (primary, secondary and tertiary)?
2. What are the sociodemographic and clinical characteristics of patients that may influence results regarding measurement of clinical and organizational quality indicators of acute stroke care?

Research hypotheses

1. Results highlight gaps between guidelines and practice following measurement of clinical and organizational quality indicators during acute management of patients with ischemic stroke.
2. Gaps between guidelines and practice resulting from measurement of the clinical and organizational quality indicators of acute stroke care may present similarities or differences between types of hospital centers.
3. Some of patients' clinical and sociodemographic characteristics influence the achievement of the clinical and organizational quality indicators of acute stroke care.
4. Patients' sociodemographic and clinical characteristics identified as influencing the achievement of clinical and organizational quality indicators may vary depending on types of centers.

3. Methodology

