3.1 Type of study

To meet the objectives of the research questions, a retrospective descriptive-correlational study will be conducted based on methods of collecting and analyzing quantitative data. The decision to conduct a retrospective study was made for two reasons: first, the nature of the data collected from records allows us to describe the current state of clinical and organizational practices during the length of patients' stay; and second, this type of study

May 2022

page 11 de 48

[name], [name], [name]

allows for the inclusion of a sample of patients hospitalized during a fixed six-month period. Finally, the feasibility of a retrospective study was considered within the context of a doctoral project with limited resources, time and budget.

In keeping with these considerations, the present study involves a multicentric investigation to take place in three differently designated Quebec hospitals in terms of stroke care. The choice of a multicentric study is based on using a larger sample of patients from different areas to obtain a broad overall view of clinical and organizational practice in stroke management in Quebec. In this study, the primary care center is a multi-vocational center including hospital care that is located in a remote area. The second participating center is a secondary care university hospital that plays an important role in the optimization of stroke care and services throughout its territory given its status as a regional center. The third hospital targeted by the study is a specialized tertiary care center which is nationally recognized for stroke treatment and performs the most thrombectomies in Quebec.

Having different and welldefined missions, these centers maintain an interdependent relation through the offer of proposed care and services. Notably, the patients from the primary care center requiring a thrombectomy are generally transferred to the tertiary center participating in this study to receive treatment. Additionally, although the tertiary care hospital is a thrombectomy center, the patients transferred there must also be returned to the secondary care referral center quickly after treatment to begin rehabilitation as early as possible. Since the majority of guidelines apply in all types of centers irrespective of where the patient is managed, each center must self-compare regarding the achievement of quality indicators.

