3.3 Sample

3.3.1 Sampling methods

A random sample composed of the health records of patients hospitalized during a fixed period who meet inclusion and exclusion criteria will be included in the study. The list of randomly selected records of patients admitted to hospital for ischemic stroke in each of the participating centers during the six months prior to the date of approval by the Research Ethics Board (REB) will be transmitted by the archives service to the principal investigator. Data collection based on health records relative to clinical and organizational quality indicators will be performed by the principal investigator and a research assistant if needed. Additionally, the principal

investigator will collect data on the characteristics of each hospital center by consulting the health professionals and managers available at the time of observation and data collection.

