3.3.2 Sample size

Calculation of number of records aims for a certain representativity of the target population at the time of data collection. Given that about 660 patients are hospitalized each year with ischemic stroke in the three centers under study - 400 in the tertiary center, 250 in the secondary center and 12 in the primary center - and the data were collected over a period of 6 months, the sample size is estimated to be some 130 health records, i.e., about 75, 45 and 8 to 10 records respectively. A power calculation in G*Power on analyses of group averages indicates this sample size is largely sufficient to have a power of 95 %, an alpha set at 0.05 and a minimal size effect of 0.5. When the size effect is not known, a minimal size effect of 50 % is acceptable (Julien, 2019). However, a first phase test will be performed with the health records of patients (n =6) hospitalized prior to the date set for the start of data collection to evaluate the average time required to analyze a record. This phase test will be performed on three health records from the secondary center and three from the tertiary center. Finally, this phase will enable needed adjustments to be made regarding implementation of research within the context of a doctoral study. Additionally, the principal investigator will have access to resources to validate the statistical analysis plan for the study duration.

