3.5 Projected statistical analyses

In response to the first research question, descriptive analyses will be conducted based on measurement of the clinical and organizational quality indicators identified in the acute phase. Medians and interquartile ranges, means and standard deviations and proportions will be used to describe performance of care and services for each center under study and comprehensively for all three centers. Additionally, a contextual description of each center will be presented using data collected on the hospitals' characteristics.

Results of the first objective will highlight indicators that do or do not meet the guidelines for quality of care for persons with ischemic stroke and their caregivers. For indicators presenting extensive data, regression analyses will be performed to identify the determinants likely to influence results regarding these indicators.

Dependent variables are clinical or organizational quality indicators, while independent variables correspond to the sociodemographic characteristics and clinical profile of patients with ischemic stroke. Type of regression analysis will vary consistent with the nature of the dependent variables (dichotomous or continuous) and their distribution (parametric or nonparametric tests).

A univariate regression analysis will first allow us to associate determinants (independent variables) with results for the indicators (dependent variables). Variables with a statistically significant association will then be introduced into a linear or logistic regression model. Additionally, these regression analyses will include

confounding variables that may also influence results from the measurement of clinical and organizational quality indicators. To be statistically significant, results must obtain a value of $p < 0.05$ and have a confidence interval of 95 %. All statistical analyses will be conducted using SPSS 28.0 software. Results will be presented comprehensively for the three centers; they may also be presented individually for the secondary and tertiary centers to see if the associations in them are similar or different. If the number of records in one of these hospitals is not enough for statistical power, the analysis will not be performed.

4. Consent process

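### Hypothesis 2 cannot be contradicted by any result, and the question 1 summaries carry no measure of precision although they come from a sample and are used to mark indicators as meeting guidelines or not

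*Protocol*

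**What the plan says.** - Section 2, research hypotheses: hypothesis 2 states that gaps between guidelines and practice "may present similarities or differences between types of hospital centers".
- Section 3.1: guidelines mostly apply in every type of centre, so "each center must self-compare regarding the achievement of quality indicators".
- Section 3.3.1: the data are "A random sample composed of the health records of patients hospitalized during a fixed period", so not every eligible record is read.
- Section 3.3.2: yearly admissions are 400 (tertiary), 250 (secondary) and 12 (primary). Planned numbers are "about 75, 45 and 8 to 10 records respectively", about 130 in total. The size is justified by a power calculation on group averages.
- Section 3.5, question 1: "Medians and interquartile ranges, means and standard deviations and proportions will be used to describe performance of care and services", and this is done "for each center under study and comprehensively for all three centers". No interval and no between-centre contrast is named.
- Section 3.5, use of these summaries: "Results of the first objective will highlight indicators that do or do not meet the guidelines for quality of care".
- Section 3.5, later paragraphs: the 5% significance level and the 95% confidence interval appear with the regressions on patient characteristics, which serve question 2. Optional separate results for the secondary and tertiary centres concern those associations (hypothesis 4), not indicator achievement.
- Appendix 1: several indicators have time windows (4, 24 or 48 hours, 7 or 30 days), but none has a target proportion.

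**The concern.** A hypothesis that is confirmed both by similarity and by difference tells the reader nothing once the data are in, and no listed analysis estimates how far the centres differ. The nearest thing to an answer is the set of per-centre columns placed side by side.

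Those columns are sample estimates. Standard deviations and interquartile ranges describe spread between patients, not how well a proportion or mean is known. The plan nevertheless draws conclusions from them. Section 3.5 sorts indicators by whether guidelines are met. Section 8 promises to point out the best and worst results and the indicators that vary or need improvement. Section 8.3 takes the results to local and regional care teams. If sampling error is of the same order as the gaps being discussed, noise could be passed on as a care gap or a difference between hospitals.

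**Working it through.** **Reproducing the plan's figures (section 3.3.2).** Admissions: 400 + 250 + 12 = 662 a year, or 331 in six months (200, 125 and 6 by centre). Planned records: 75 + 45 + 8 to 10 = 128 to 130. Sampling fraction: 130/331 = 39%. The statement of 95% power at an effect size of 0.5 reproduces for a three-group analysis of variance with f = 0.5 (about 66 records needed). It does not reproduce for a two-group comparison with a standardized mean difference of 0.5 (105 per group, two-sided). The protocol does not say which was meant. Either way the calculation concerns a comparison of means that section 3.5 does not list, and it says nothing about the precision of an indicator.

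**Precision by centre.** Half-width = 1.96 × √(p(1 − p)/n). For the difference, the two half-widths are combined as the root of the sum of squares. If the target of inference is only the patients admitted in the six months, multiply each half-width by √((N − n)/(N − 1)):
- tertiary: √(125/199) = 0.793
- secondary: √(80/124) = 0.803

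The protocol gives no expected value for these hospitals. I assume p = 65%, which is the dysphagia-screening figure the introduction quotes from one regional hospital, and show 50% and 80% as a range.

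At 65%:
- tertiary: 1.96 × √(0.2275/75) = 10.8 points; corrected 10.8 × 0.793 = 8.6
- secondary: 1.96 × √(0.2275/45) = 13.9 points; corrected 13.9 × 0.803 = 11.2
- difference: √(10.8² + 13.9²) = 17.6 points; corrected √(8.6² + 11.2²) = 14.1

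| Assumed p | Tertiary (n = 75) | Secondary (n = 45) | Difference |
|---|---|---|---|
| 50% | 11.3 (corrected 9.0) | 14.6 (11.7) | 18.5 (14.8) |
| 65% | 10.8 (8.6) | 13.9 (11.2) | 17.6 (14.1) |
| 80% | 9.1 (7.2) | 11.7 (9.4) | 14.8 (11.8) |

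**How often noise looks like a gap.** Suppose both centres truly achieve 65%. The standard error of the difference is 17.6/1.96 = 9.0 points, so an apparent gap of 10 points or more is 10/9.0 = 1.11 standard errors and arises in about 27% of samples. With the correction the standard error is 14.1/1.96 = 7.2, the ratio is 1.39 and the figure is about 16%.

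**Against a target.** An observed 80% has a 95% Wilson interval of 69.6% to 87.5% for 60/75 and 66.2% to 89.1% for 36/45. An illustrative target of 85% lies inside both, and one of 95% lies outside both. The corrected half-widths at 80% (7.2 and 9.4 points) still exceed the 5-point distance to 85%. Large shortfalls can be called and near-target ones cannot.

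**Primary centre.** Twelve admissions a year give about 6 in six months, fewer than the 8 to 10 records planned. If there are only about 6 and all are read, that is a full count for the period and sampling error does not apply.

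**The case against.** The study is descriptive. Question 1 asks what performance is, not whether centres differ, and intervals and table layouts are often left to a statistical analysis plan, which section 3.3.2 mentions and which is not shown here. This has weight and limits the point. But the wording of hypothesis 2 is fixed in the protocol, and section 3.5 itself lists the summaries and the use to be made of them.

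Some stronger readings a reader might infer do not hold:
- *The study cannot say whether centres differ or a target is missed.* Too strong. Large gaps would be plain, anyone can form an interval from reported counts, and section 3.5 also has pooled summaries and regressions with intervals. Those regressions might include centre, which Appendix 2 files under sociodemographic characteristics, but section 3.5 does not say so.
- *Indicators are judged on the point estimate alone.* Section 3.5 states no decision rule, so this would be read into its silence.
- *Section 3.1 forbids comparing centres.* It asks for self-comparison but does not say that nothing else will be done. Measuring each centre against guidelines and then setting the gaps side by side is a possible reading. The sections sit badly together, but they do not flatly contradict each other.
- *An interval on 6 primary-centre records shows its imprecision.* That number conflicts with the 8 to 10 planned and may be a full count.
- *An indicator should be called below target only if its interval excludes the target.* Appendix 1 supplies no target proportions, and such a rule would flag small centres least.
- *Hypothesis 2 should assert that centres differ.* That would turn a descriptive aim into a test across up to 29 indicators. It would have about 58% power for 50% against 70% (75 and 45 records, two-sided 5%).

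**Conclusion.** The point holds in a limited form and should be acted on. Hypothesis 2 is compatible with every outcome and no analysis in section 3.5 addresses it. The question 1 summaries are given without precision although about 39% of eligible records are read and the results are used to mark indicators against guidelines.

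With the planned 75 and 45 records, uncertainty at an assumed 65% is about 11 and 14 points by centre and 18 for the difference. It is about 9, 11 and 14 if the inference is confined to the six-month admissions. Differences of that order may be sampling error, while clearly larger ones would stand out. These figures assume simple random sampling within centre and complete data on the indicator; missing entries or smaller denominators would widen them.

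With one hospital per designation, no interval can support a statement about types of hospital.

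**What to change.** 1. **Section 3.5, precision.** Report a 95% interval for each patient-level indicator by centre: Wilson for proportions, and a suitable interval for means or medians of times and lengths of stay (for example indicators 2, 4 and 8). Give none for indicators 5 and 6, which are centre-level telehealth measures. Say whether a finite-population correction is applied.
2. **Section 3.5, contrast.** Report the secondary-minus-tertiary difference with its 95% interval, labelled as a descriptive estimate about these two hospitals and not about hospital types.
3. **Primary centre.** Show counts only, and reconcile the 8 to 10 planned records with 12 admissions a year.
4. **Met or not-met statements.** Present each with its interval and the target used, because Appendix 1 gives no target proportions.
5. **Sections 2 and 3.1.** Restate hypothesis 2 as an estimation aim (the size of the secondary-tertiary difference in indicator achievement) or drop it, and make section 3.1 agree with the choice.

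The cost is some rewording and a few table columns, with no new data. The downside is that some near-target indicators will be reported as inconclusive.
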